| 
DATA ANALYSIS
 | 
Demographics and clinical characteristics will be summarized for all patients enrolled as well as grouped separately for patients continuing treatment with Valchlor versus patients who are newly initiating Valchlor. Use of prior treatments and past methods of assessing response will similarly be analyzed separately for the two groups. Treatments individually and in combination will be reported in percentage terms, by visit, stratified by newly initiating patients and continuing patients to identify treatment patterns.
 
Analyses of response, based on a particular measure of response, will be limited to patients for whom that measure was reported. Therefore, patients with reported data will be summarized also for patients without any reported data with respect to demographics and pre-treatment clinical status to identify potential biases. Rates of on-study hospitalization and emergency room visits will be computed as the utilization counts divided by on-study days. The summary of response rates will be tabulated and the definition of response will be detailed in the Statistical Analysis Plan.
 
The frequency and percentage of patients experiencing any AEs or SAEs will be summarized by system organ class and preferred MedDRA terminology. SAEs requiring hospitalizations and fatal SAEs will be displayed in patient listings.
 
At each visit performed during the observation period (1st, 2nd, etc.), the VAS for pruritus, the three scales of the Skindex-29 and the MF/SS-CTCL questionnaires will be computed for patients who are and are not responders. These descriptive cross-sectional comparisons are intended to assess burden of disease in a Valchlor-treated cohort over time.
 |
| 
MILESTONES
 | 
First patient, first visit: Q4 2014
 
Last patient, first visit: Q3 2017
 
Last patient, last visit: Q3 2019
 |

| | |
|--------------------|---|
| DATA OWNERSHIP | Actelion Pharmaceuticals US, Inc. |
| STUDY COMMITTEE(S) | The Scientific Committee will consist of 4–6 key opinion leaders in the field of MF-CTCL who will provide scientific input on the MF-CTCL Study protocol and review study data. |

PROTOCOL

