5.7.5 Adverse events

The frequency and percentage of patients experiencing any on-study AEs, SAEs, or death will be summarized by system organ class and preferred MedDRA terminology. Additional detail for AEs of special interest (e.g., dermatitis) will be summarized separately. SAEs will be displayed in patient listings, both including and excluding events that were not concurrent with Valchlor exposure. The definition of an on-study event is one that occurs on the day of enrollment or later, but before the date of study discontinuation or completion.

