## **Patient Disposition and Reason for Discontinuation**

The number and percentage of patients discontinuing from the study, along with the number and percentages of the reasons for discontinuation will be presented in a table. In addition, a listing of all patient disposition, including completed patients and discontinued patients, will be provided.

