Table 27b. Change from baseline at each timepoint in PRO questionnaires: SkinDex-29

Table 27c. Change from baseline at each timepoint in PRO questionnaires: MF/SS CTCL QOL instrument

Table 28. Other Treatments for MF-CTCL

Therapy	Prior to Mechlorethamine Treatment (N=289) (N/%)	During Mechlorethamine Treatment (N=289) (N/%)	Mean Treatment Duration During PROVe Study
Skin-directed therapy, n (%)	226 (78)	125 (43)	
Phototherapy	143 (49.5)	33 (11)	
UVB/Narrow Band-UVB			
PUVA/UVA-1			
ECP – Therakos (extracorporeal photopheresis)			
Radiation therapy (TSEB)	38 (13)	16 (5.5)	
Chemotherapy (topical) Name the 1 agent	4 (1)	1 (<1)	
Corticosteroids (topical)	165 (57)	88 (30)	
See full list below for reference only			
Retinoid (topical)	39 (13.5)	9 (3)	
Bexarotene			
tazarotene			
adapalene			
Imiquimod (topical)	18 (6)	7 (2)	
Systemic therapy, n (%)	83 (29)	47 (16)	
Chemotherapy (systemic)	18 (6)	11 (4)	
methotrexate			
CHOP (cyclophosphamide + vincristine + Adriamycin + prednisone)			
Liposomal doxorubicin			
gemcitabine			
pentostatin			
Monoclonal Antibodies			
Brentuximab			
Alemtuzamab			
Mogamulizumab			

Interferon			
Retinoids (systemic)	59 (20)	36 (12.5)	
Bexarotene			
HDAC Inhibitors	20 (7)	6 (2)	
Vorinostat			
Remetinostat			
Romidepsin			
Panobinostat			

Listing 1: Serious Adverse Events

Patient ID, AE Date, System Organ Class, Preferred Term, Verbatim Term, Completed/Discontinued, Reason for Discontinuation

Listing 2: Serious Adverse Events Resulting in Death

Patient ID, AE Date, System Organ Class, Preferred Term, Verbatim Term

Listing 3: Adverse Events

Patient ID, AE Date, System Organ Class, Preferred Term, Verbatim Term

Listing 4: Pregnancy

Patient ID, Age, Sex/Gender, Positive Pregnancy Confirmation

Listing 5: Secondary Exposures

Patient ID, Age, Sex/Gender, Positive Secondary Exposure

Listing 6: Patient Disposition

Patient ID, D/C Date, Reason for D/C

Listing 7: Demographic and Baseline Characteristics by Subject and Treatment Group

Patient ID, Age, Gender, Race, MF Stage, Date of First Diag, CAILS, SWAT, %BSA

Listing 8: Efficacy Data (CAILS, SWAT Scores and % Body Surface Area with Response Assessment) by Subject and Treatment Group

Patient ID, Age/Gender/Race MF Stage, Visit Dt, CAILS, CAILS Change, CAILS Response, SWAT, SWAT Change, SWAT Response, %BSA, %BSA Change, %BSA Response

Listing 9: Subjects Who Reported Adverse Events

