Patient ID, Age/Gender/Race, MF Stage, AE PT, Onset Dt, Duration, Serious, Rel to Med, Intensity, Action Taken

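### The SAP omits the protocol's SAE listing with and without events outside Valchlor exposure, and Listings 1 and 2 have no field for exposure at onset

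*SAP*

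**What the plan says.** Protocol 5.7.5 states the requirement: "SAEs will be displayed in patient listings, both including and excluding events that were not concurrent with Valchlor exposure". The same section defines an on-study event as "one that occurs on the day of enrollment or later, but before the date of study discontinuation or completion". That definition depends on study dates, not on Valchlor use, so the two-version listing is where the protocol separates exposed from unexposed SAEs.

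The SAP does not carry this forward. Its Statistical Methods section mentions a patient listing only for SAEs that result in death. Appendix A has one listing of all SAEs (Listing 1), with columns "Patient ID, AE Date, System Organ Class, Preferred Term, Verbatim Term, Completed/Discontinued, Reason for Discontinuation", and one of fatal SAEs (Listing 2), with columns "Patient ID, AE Date, System Organ Class, Preferred Term, Verbatim Term". Neither comes in two versions.

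The data needed for the split are collected. SAP Table 1 (footnote) and the section on Valchlor dosing regimens record start and stop dates, including short gaps such as drug holidays. The section on exposure definitions uses the same treatment log.

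**The concern.** Protocol 5.1 keeps patients in the study after they stop Valchlor, and the SAP's Analysis Populations section says that patients stopped the gel, switched therapy and remained under observation. Some listed SAEs may therefore fall in a drug holiday, shortly after stopping, or later on another therapy. A listing exists for case-by-case safety review, and exposure at onset is basic to that review. Protocol 7.1.3 itself names temporal relationship as a guide to relatedness, so a reader needs the timing to check the investigator's judgement.

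Programmers work from the SAP. Followed as written, it drops a safety output that the protocol names. The SAP gives no reason, although it does give one when it drops the new-versus-continuing analyses. If the split is added later without a rule for concurrence, that rule will be set after the events have been seen.

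**Working it through.** The plan states no figure for this point. The check compares listing columns with the protocol requirement, then bounds the size.

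**Columns that give Valchlor dates or on/off status at onset**

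- Listing 1 (all SAEs): 0 of 7. Completed/Discontinued is not defined in the shell. The SAP's disposition section uses the term for leaving the study: "The number and percentage of patients discontinuing from the study, along with the number and percentages of the reasons for discontinuation". Even if it meant stopping Valchlor, Listing 1 gives no date for it.
- Listing 2 (fatal SAEs): 0 of 5.
- Listing 6 (disposition): "Patient ID, D/C Date, Reason for D/C". By the disposition section, this date is for discontinuing the study.
- Listing 9 (AEs by subject): "Patient ID, Age/Gender/Race, MF Stage, AE PT, Onset Dt, Duration, Serious, Rel to Med, Intensity, Action Taken". It adds seriousness, relatedness and action taken, but no Valchlor dates and no exposure status.

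SAE listing versions split by concurrence: 2 required by the protocol, 0 planned in the SAP.

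**Rule for concurrence.** The SAP gives none. Protocol 5.3.2 leaves drug holidays out of summed exposure time, and the SAP sums dosed days for patients who restart, but neither says how an event in a gap is classed. Date imputation matters too. A missing day of discontinuation becomes the 15th, so the true date may be up to 15 − 1 = 14 days earlier or 31 − 15 = 16 days later. That is about half of a 30-day window.

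**Which post-stop events are collected.** The documents conflict.

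- The SAP's Assessment Schedule text has related and unrelated events collected during use and more than 30 days after stopping.
- The Table 1 footnotes in both documents, and Protocol 7.1.2 and 7.2, limit new events beyond 30 days to those with a possible causal link to Valchlor.

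**Size.** Inputs: 15-20% of patients stopped and switched (SAP Analysis Populations; base not stated), and a maximum follow-up of 2 years, or 730 days (Protocol 5.1).

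- Patients, if the share applies to the 289 in SAP Table 28: 0.15 × 289 ≈ 43; 0.20 × 289 ≈ 58.
- Post-stop share of patient-time under the 30-day rule: 0.15 × 30/730 ≈ 0.6%; 0.20 × 30/730 ≈ 0.8%. With 1-year follow-up, as for patients who finished under the original protocol: 0.15 × 30/365 ≈ 1.2%; 0.20 × 30/365 ≈ 1.6%.
- Post-stop share if all post-stop time is open to collection and stops are uniform, so that half of each stopper's follow-up is off drug: 0.5 × 15% = 7.5%; 0.5 × 20% = 10%.

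Drug holidays, and late events judged possibly related, add an unknown amount to the 30-day figures.

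**The case against.** The strongest reply is that this is a gap in descriptive listings that affects no estimate and can be closed from data in hand. That is correct, and it limits the weight of the point. Four stronger readings are tempting, and the documents do not support them.

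- A reader might infer that the split cannot be produced. It can: event dates and Valchlor start and stop dates, gaps included, are collected. What is missing is the specification.
- A reader might infer that off-drug SAEs are presented as on-drug. No listing labels any event as on-drug; status is left undetermined. Listing 9 gives some context and can be matched to Listing 1 by patient, preferred term and date.
- A reader might take 7.5-10% to mean that about 1 in 10 listed SAEs is off-drug. That needs the Assessment Schedule text to override four other places in the documents, uniform stopping, and equal SAE rates on and off drug. No count of off-drug SAEs is given.
- A reader might say that the synopsis is also breached, since it promises that "SAEs requiring hospitalizations and fatal SAEs will be displayed in patient listings". Listing 1 shows every SAE, so those leading to hospitalization are displayed. The protocol does not ask for a seriousness-criterion column.

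What the reply does not answer is the omission itself. Relatedness and action taken are not exposure at onset, and no listing supplies it.

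**Conclusion.** The point holds as an omission. Protocol 5.7.5 names a two-version SAE listing, the SAP does not plan it, and no field in Listings 1, 2, 6 or 9 gives Valchlor exposure at onset. How many SAEs are affected is unknown. The post-stop share of patient-time is about 0.6-0.8% if the 30-day rule governs, before holidays and late related events, and up to about 7.5-10% if the Assessment Schedule text governs. Both ranges rest on reading the 15-20% as a share of all patients. The lower also assumes 2-year follow-up and the upper assumes uniform stopping. These are shares of time, not of SAEs. The change should be made because it restores a safety output that the protocol names, at low cost; it alters no endpoint, estimate or error rate.

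**What to change.** 1. Produce Listing 1 in two versions: all on-study SAEs, and SAEs concurrent with Valchlor.
2. Add to Listings 1 and 2 a flag for Valchlor status at onset and the days since last Valchlor use, both derived from the treatment log.
3. State in the SAP how *concurrent* treats drug holidays, the 30 days after stopping, and discontinuation dates imputed to the 15th.
4. Reconcile the SAP's Assessment Schedule text with the Table 1 footnotes in both documents and with Protocol 7.1.2 and 7.2, so that it is clear which post-discontinuation events are collected and can appear in the listings.

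Columns for relatedness and seriousness criterion in Listings 1 and 2 are optional.

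The cost is a small amount of shell and programming work. No new data are needed for the listings.
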